#### ***6.9.4 Contraception***

Potential postmenopausal status for female patients will be confirmed with a screening serum follicle-stimulating hormone (FSH) level  $> 40$  mIU/mL. Rules for contraception during study participation are outlined in the inclusion criteria, see [Section 5.1](#).

#### **6.10 Treatment compliance**

Since all treatments are administered at the clinical site by site personnel, the Investigator or designee must maintain accurate records of all study treatments, including dates of study drug receipt, quantities received and dispensed, and batch/lot numbers. In addition, the study treatment must be noted in the patient's medical records and eCRF, with the date and time of administration and dose of each study treatment.

## 7 STUDY ASSESSMENTS AND PROCEDURES

### 7.1 Study schedule

Study assessments and procedures, and their timings (including visit windows) are summarized in the Study Schedule ([Error! Reference source not found.](#)). As protocol exemptions are not foreseen in this trial, except in case of immediate safety concerns, any deviation from the planned study schedule should be discussed with the Sponsor immediately upon occurrence or awareness to determine if the patient should continue, or discontinue, the study treatment. Adherence to the study design requirements, including those specified in the Study Schedule, is essential and required for adequate study conduct.

### 7.2 Screening period #1

The trial will include a 2-stage consent and screening procedure (see [Section 4.2](#)).

The initial minimized consent, and screening period #1, is related to the procedure of HLA-testing, and before testing also establishing based on available information that the patient has eligible ACC or MPP, and an age  $\geq 18$  years (inclusion criteria #1 to 5; see [Section 5.1](#)).

The following will be done during screening period #1:

- study ICF procedure for consent #1, and
- eligibility ascertained for inclusion criteria #1 to 5 (#1 to 3 as applicable depending on stage of trial conduct and patient tumor disease).

[figure not shown]
HLA-testing can be performed within the scope of the trial, but HLA-information based on testing before the screening period is also acceptable (no time limit is applied; patients with prior hematopoietic stem cell transplantation are not eligible for the trial).

HLA-testing will be performed locally; information regarding the local lab, including methods used will be collected. Low resolution HLA-typing (i.e. genotyping of the HLA-A loci 2 to 2 digits) is considered satisfactory for trial enrolment. However, 4-digit resolution typing is preferred; also, a more complete HLA-typing is preferred.

All information available regarding the individual patient MHC-composition will be collected, i.e. also information beside the HLA-A type. Patients who are not HLA-A2 positive will be assigned a “screen failure”-status and not continue any further trial procedures; such patients will be replaced.

[figure not shown]
Protocol No: EOADR1-19  
EudraCT: 2019-003396-19

CONFIDENTIAL

[figure not shown]
[figure not shown]
Protocol No: EOADR1-19  
EudraCT: 2019-003396-19

CONFIDENTIAL

[figure not shown]
[figure not shown]
Protocol No: EOADR1-19  
EudraCT: 2019-003396-19

CONFIDENTIAL

[figure not shown]
Protocol No: EOADR1-19  
EudraCT: 2019-003396-19

CONFIDENTIAL

[figure not shown]
Protocol No: EOADR1-19  
EudraCT: 2019-003396-19

CONFIDENTIAL

Protocol No: EOADR1-19  
EudraCT: 2019-003396-19

CONFIDENTIAL

### 7.3 Screening period #2

The second stage of the consent procedure, and screening period #2, will be related to all other aspects of the trial, except those outlined in [Section 7.2](#) (for remaining inclusion/exclusion criteria see [Section 5.1](#) and [Section 5.2](#)). All timelines included in the protocol and related to the signature of the ICF are referring to the signature of this second part of the ICF. All evaluations must be completed and reviewed within the timeframe defined in the Study Schedule ([Error! Reference source not found.](#)) to confirm that potential patients meet all eligibility criteria. The Investigator will record adequate details of all patients screened and to confirm eligibility, or record reasons for screen failure, as applicable (see [Section 5.3.2](#)).

Procedures conducted as part of the patient's routine clinical management (e.g. blood count) and obtained before signing the consent form may be utilized for screening purposes, provided the procedure met the protocol-specified criteria. Results obtained also the week before screening started [REDACTED] can be used for study purposes provided the study Medical Monitor's approval is granted; this also includes an acceptable time window for the screening/baseline CT.

All screening examinations will be performed locally, at the site or an affiliate site due to e.g. the location of the site and the patient.

The maximum amount of blood to be taken from each patient at screening, or over the duration of the study, including any extra assessments that may be required, will not exceed volumes as stated by local regulations. Repeat, or unscheduled samples, may be taken for safety reasons, or for technical issues with the samples.

[figure not shown]
Patients who do not fulfill all eligibility criteria will be assigned a "screen failure"-status and not continue any further trial procedures; such patients will be replaced.

The following will be done during screening period #2:

- study ICF procedure for consent #2,
- eligibility ascertained for inclusion and exclusion criteria (see [Section 5.1](#) and [Section 5.2](#)),
- documentation of;
  - patient demographics (age, ethnicity, race),
  - extended history of oncology disease(s), including dates of diagnosis and treatments history,
  - medical history of other (than oncology) disease processes (all prior significant illnesses that are relevant to patient safety or that the patient has experienced prior to screening; especially history of anaphylaxis or other reactions following vaccination, and history of immune deficiencies), and concomitant illness (illnesses present at the time of informed consent are to be regarded as concomitant illnesses; illnesses first occurring or detected during the study and/or worsening of a concomitant illness during the study are to be documented as AEs on the eCRF and as SAEs if case seriousness criteria are met),
  - medications, including vaccines, and other relevant treatments (e.g. surgeries) during 28 days prior to signing informed consent; all applicable treatments (systemic and local), also before 28 days prior to informed consent signing, for oncology disease(s) will be collected,
  - concomitant medications/treatments,

- measurement/assessment of;
  - height and weight,
  - ECOG performance status (see [Section 12.2](#)),
  - vital signs including temperature, blood pressure (BP), and heart rate (HR) (BP and HR will be measured according to local standard practice); if systolic BP is below 100 mmHg or above 150 mmHg, and/or diastolic BP is below 50 mmHg or above 90 mmHg, the measurement will be repeated; the HR measurement will be repeated when below 50 bpm or above 100 bpm,
  - major body systems via physical examination; general appearance, skin, neck (incl. thyroid), ENT (ears, nose, throat), lungs, heart, abdomen, lymph nodes (all major stations palpable), extremities, neurology, and other sites as applicable (i.e. symptom directed),
- safety blood samples for hematology, coagulation, serum chemistry, urinalysis, hormones, and virus serology to be performed and evaluated locally, detailed as;

A large black rectangular box used to redact sensitive information.

- a 12-lead electrocardiogram (ECG) will be recorded according to local site standard procedures, and
- adverse events will be reported according to NCI-CTCAE v5.0; documentation of AEs/SAEs starts after trial consent has been given by the patient.

#### 7.4 Visits during study treatment

Note, measurements/assessments/sampling as outlined below are to be done before administration of study treatments if scheduled for the same day, if no other specific order of events is defined (e.g. for DTH-testing there is a special procedure and timing as outlined in [Section 6.6.3](#)).

##### 7.4.1 Visits during EO2401 priming phase; V1, V2, V3, V4, and V5

[figure not shown]
Visit 1 (V1) must be performed within [REDACTED]  
screening/baseline CT.

Visits V1 to V4 are planned to be performed every 2 weeks [REDACTED] and V5 2 weeks +/- [REDACTED] after V4.

The following will be done during the visits [REDACTED]

- at V1, V2, V3, and V4;
  - administration of EO2401 and nivolumab should be done per allocated treatment cohort [REDACTED]
  - documentation of concomitant medications/treatments,
  - measurement/assessment of;
    - weight, and ECOG performance status (see [Section 12.2](#)),
    - vital signs, and major body systems via physical examination, as outlined in [Section 7.3](#),
    - safety blood samples for hematology, coagulation, serum chemistry, and urinalysis, as outlined in [Section 7.3](#),
  - adverse events will be recorded according to NCI-CTCAE v5.0 (AEs will be monitored for the whole duration of the trial, but assumed recorded at visits for treatments, except in cases where the seriousness demands more immediate reporting, see [Section 8](#)),

- at V1, V2, V3, V4, and V5;

[figure not shown]
- assessment of serum cortisol, TSH, and free T4, as outlined in [Section 7.3](#)

- for women of childbearing potential, highly sensitive serum pregnancy test,

- assessment of a 12-lead ECG, as outlined in [Section 7.3](#),

[figure not shown]
- a CT for tumor status assessment should be performed and tumor response assessment made, as outlined in [Section 7.7](#).

[figure not shown]
#### **7.4.2 *Visits during EO2401 boost period; from V6 until treatment discontinuation***

From visit V6 and onwards, [REDACTED]

[figure not shown]
The following will be done during the visits:

- administration of EO2401 and nivolumab should be done per allocated treatment cohort [REDACTED]

[figure not shown]

[figure not shown]
- at the visits for study treatment administration the following will also be done;
  - documentation of concomitant medications/treatments,
  - measurement/assessment of;
    - weight, and ECOG performance status (see [Section 12.2](#)),
    - vital signs, and major body systems via physical examination, as outlined in [Section 7.3](#),
    - safety blood samples for hematology, coagulation, serum chemistry, and urinalysis, as outlined in [Section 7.3](#),

- adverse events will be recorded according to NCI-CTCAE v5.0 (AEs will be monitored for the whole duration of the trial, but assumed recorded at visits for treatments, except in cases where the seriousness demands more immediate reporting, see [Section 8](#)),

[figure not shown]
- for women of childbearing potential, highly sensitive serum pregnancy test,

- assessment of serum cortisol, TSH, and free T4, as outlined in [Section 7.3](#),

- a CT for tumor status assessment should be performed and tumor response assessment made, as outlined in [Section 7.7](#).

## 7.5 Visits during post-treatment follow-up

### 7.5.1 Post-treatment visit for safety assessment; Vn+1

A post-treatment safety assessment visit should be performed 30 days after the last study treatment has been administered.

The following will be done during the visits:

- documentation of concomitant medications/treatments,
- measurement/assessment of:
  - weight, and ECOG performance status (see [Section 12.2](#)),
  - vital signs, and major body systems via physical examination, as outlined in [Section 7.3](#),
  - safety blood samples [REDACTED]
  - for women of childbearing potential, highly sensitive serum pregnancy test,
  - assessment of a 12-lead ECG,
- adverse events will be recorded according to NCI-CTCAE v5.0 (AEs will be monitored for the whole duration of the trial, but assumed recorded at visits for treatments, except in cases where the seriousness demands more immediate reporting, see [Section 8](#)), and

### 7.5.2 Post-treatment follow-up before assessed progressive disease; Vnn

Patients who are discontinuing all study treatment without having had confirmation of progressive disease according to iRECIST criteria will be followed [REDACTED] after the latest performed CT assessment during the time period they received study treatment.

At these [REDACTED] timepoints the following will be done:

- a CT for tumor status assessment should be performed and tumor response assessment made, as outlined in [Section 7.7](#),

- documentation of safety; after the post-treatment visit for safety assessment (see [Section 7.5.1](#)) has been made, only SAEs with plausible causal relationship with trial treatment will be documented (in addition, in case of death, an as precise cause of death as possible is going to be documented), and
- if applicable, collection of information regarding further anti-cancer treatments.

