### 8.3 Safety monitoring periods

#### 8.3.1 Reporting

In patients exposed to study treatment, the following must be reported from the date of the patient's signing the ICF until 30 days after the final administration of study treatment:

- AEs regardless of their causal relationship to study treatment,
- SAEs without a plausible causal relationship to study treatment, and
- pregnancy of the patient.

SAEs with a plausible causal relationship to study treatment must be reported from the date of the patient's signing the ICF until indefinitely (regardless of the time elapsed from the final study treatment administration).

In addition, for consistency with nivolumab clinical trial protocols as advised by Bristol-Myers Squibb (marketing authorization holder for nivolumab), collect all non-serious adverse events (not only those deemed to be treatment-related) continuously during nivolumab treatment periods and for a minimum of 100 days following discontinuation of nivolumab treatment. The most conservative approach (longest follow-up) emanating from the two principles (30 days and specifics per above paragraph versus 100 days following discontinuation of nivolumab treatment) should be followed for nivolumab.

In patients not exposed to study treatment, the reporting period for AEs (including SAEs regardless of causal relationship) starts with signature of the ICF and ends:

- the date of the Investigators assessment of "screen failure"-status (see [Section 5.3.2](#)), or
- the date of the patient's consent withdrawal.

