## 8.5 Reporting by the investigational site

### 8.5.1 Adverse events

Any AE (including SAEs), whether, or not considered to be causally related to the trial medication and regardless of its seriousness, must be reported (described and recorded) in the AE section of the patient's eCRF on an ongoing basis.

A pre-existing condition is a clinical condition (including a condition being treated) that is diagnosed before the patient signs the ICF and that is documented as part of the patient's medical history; any clinically significant worsening of a pre-existing condition constitutes an AE. Also, any recurrence of a pre-existing condition is an AE.

The questions concerning whether the condition existed before the start of the active phase of the study and whether it has increased in severity and/or frequency will be used to determine whether an event is a TEAE. An AE is considered to be treatment-emergent if it is not present when the active phase of the study begins and is not a chronic condition that is part of the patient's medical history, or it is present at the start of the active phase of the study or as part of the patient's medical history, but the severity or frequency increases during the active phase. The active phase of the study begins at the time of the first dose of the study drug. The active phase of the study ends 100 days after the last study drug administration [REDACTED]

A standardized question such as "Have you had any health problems since your last visit or since you were last questioned?" will be given by the Investigator or the investigational site personnel at each contact with the patient.

[figure not shown]
Progression of the underlying disease or an AE unequivocally (without doubt) related to the progression of the underlying disease, regardless of its outcome or seriousness criteria, does not need to be reported as an AE/SAE. However, the medical conditions and underlying diseases associated with disease progression needs to be captured on the AE eCRF page (as a non-serious AE). An SAE must be reported only if there are clinical symptoms/signs that cannot be without doubt associated with the progression of the underlying disease.

Whenever possible, a diagnosis rather than symptoms should be provided (e.g. anemia instead of low Hb).

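### Protocol 7.5.2 and 7.5.3 limit new adverse-event recording after the 30-day visit to related SAEs, which conflicts with the 100-day collection rule in 8.3.1 and falls short of the 100-day TEAE window in 8.5.1

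*Protocol*

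**What the plan says.** **Follow-up sections.** Protocol 7.5.1 fixes the trigger: "A post-treatment safety assessment visit should be performed 30 days after the last study treatment has been administered". Once that visit has been made, 7.5.2 (follow-up before progression) and 7.5.3 (survival follow-up) both state that "only SAEs with plausible causal relationship with trial treatment will be documented". Both also ask for cause of death.

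**Reporting section.** Protocol 8.3.1 starts from a general rule: all AEs, "SAEs without a plausible causal relationship to study treatment" and pregnancies are reported "until 30 days after the final administration of study treatment", while related SAEs are reported without time limit. It then adds a nivolumab-specific rule: "collect all non-serious adverse events (not only those deemed to be treatment-related) continuously during nivolumab treatment periods and for a minimum of 100 days" after nivolumab stops. It closes by saying that, for nivolumab, whichever principle gives the longer follow-up applies.

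**Counting window.** Protocol 8.5.1 defines treatment emergence by an active phase: "The active phase of the study ends 100 days after the last study drug administration". The text directly after this is redacted. SAP 7.11.2 repeats the definition with its day count redacted. SAP 6.2 treats EO2401 and nivolumab each as study drug.

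**Laboratory tables.** In SAP 7.11.3 the worst-value tables exclude baseline, and the table of maximum improvement or worsening uses post-baseline grades. The worst-CTCAE-grade table expressly includes assessments made before treatment. The shift table runs from baseline to the worst grade over the whole study and does not say whether pre-dose values count.

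**The concern.** A TEAE count is interpretable only if events are collected for as long as they are counted. Here one part of the protocol stops recording most new events at the 30-day visit, while another counts them to day 100. The loss is also selective: related SAEs are always recorded, whereas new non-serious AEs and unrelated SAEs are not.

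AE, TEAE and SAE incidences for the combination form the phase 1 primary endpoint (Protocol 3.2.1). SAP 7.11.2 tabulates serious TEAEs both overall and as related, and selective recording distorts the contrast between the two. In the randomised extension, Protocol 7.6 sets the combination's AEs beside those of the monotherapy groups, both regardless of relationship and as related events. Unequal collection windows between arms would matter there.

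The laboratory issue is smaller. A grade seen only before dosing is tabulated together with on-treatment grades, so the worst-grade table cannot be read as treatment-emergent.

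**Working it through.** The plan gives no figure to reproduce. The check sets the windows side by side and counts who falls in the gap.

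| Source | What is covered | Ends |
|---|---|---|
| 7.5.1 with 7.5.2/7.5.3 | New non-serious AEs and unrelated SAEs | 30-day visit |
| 8.3.1, general rule | All AEs, unrelated SAEs | Day 30 after last study treatment |
| 8.3.1, nivolumab rule | All non-serious AEs | At least day 100 after nivolumab |
| 8.3.1 and 7.5.2/7.5.3 | Related SAEs | No limit in 8.3.1; still recorded in 7.5.2/7.5.3 |
| 8.5.1 | TEAEs counted | Day 100 after last study drug |

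**Do the rows conflict?** For a nivolumab-treated patient with a new unrelated non-serious AE on day 60, 8.3.1 says record it and 7.5.2/7.5.3 say do not. The tie-break in 8.3.1 settles its own two principles but does not amend 7.5.2/7.5.3. The 100-day sentence names only non-serious AEs. Unrelated SAEs reach day 100 through the tie-break, which is its natural reading.

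**Length of the gap.** 100 − 30 = 70 days (days 31-100).

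**Patients** (SAP 4.2):
- Non-randomised combination: 26 + 7 + 13 + 5 = 51.
- All combination: 51 + 13 = 64.
- Any nivolumab: 64 + 4 = 68.
- All treated: 68 + 2 on EO2401 alone = 70, which agrees with the Synopsis.
- Randomised: 13 + 2 + 4 = 19.

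**If 8.3.1 was followed:** 68/70 = 97.1% have collection to day 100 after nivolumab. The visible gap is Cohort 2A-II: 2/70 = 2.9% of treated patients and 2/19 = 10.5% of randomised patients.

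**If 7.5.2/7.5.3 were followed:** the restriction applies to all 70 patients for up to 70 days each. This is an upper bound, because not every patient is alive and followed to day 100.

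**Scale, by assumption only.** Suppose a constant hazard and a proportion p of patients with a first non-serious or unrelated event by day 100. The share with onset by day 30 is 1 − (1 − p)^0.3. For p = 5% this is 1.5%, leaving 3.5 percentage points in days 31-100. For p = 30% it is 10.1%, leaving 19.9 points. The documents give no event rates, so these figures show scale and are not estimates.

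**Laboratory table.** A patient with baseline grade 2 and post-dose grades 0-1 appears as grade 2 in the worst-grade table but as an improvement of up to 2 grades in the change table. With pre-dose prevalence b and post-dose rate q, assumed independent, the displayed rate is 1 − (1 − b)(1 − q). For q = 10% and b = 5%, 10% or 20%, that is 14.5%, 19% or 28%. These inputs are also assumed.

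**The case against.** The strongest reply is that Section 8 already governs. Sections 7.5.2/7.5.3 restate the general rule of 8.3.1, which 8.3.1 then extends for nivolumab and resolves in favour of the longer period. Section 7.6 refers safety monitoring procedures to Section 8, and 8.5.1 requires any AE, related or not, to be entered on an ongoing basis. This stands as the probable intent. It does not remove the conflict for a site working from the follow-up sections, and 7.6 also refers the specific parameters to be assessed to 7.3-7.5.

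Second, 8.3.2 keeps following events already recorded, and cause of death is still collected. This also stands: only new onsets are at issue.

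Third, redactions follow the 100-day text in 8.5.1 and cover the day count in SAP 7.11.2 and the safety follow-up period in Protocol 9.2. The study schedule is not visible. A qualifier for EO2401 alone could exist, so the 2A-II gap is provisional.

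Several stronger readings are tempting, but the documents do not support them:
- A reader might infer that all 70 patients were under-recorded, or that the phase 1 primary endpoint is biased. That requires sites to have followed 7.5.2/7.5.3, which nothing in the documents shows.
- A reader might widen the gap to patients continued on EO2401 after nivolumab stopped, since the 100-day collection runs from nivolumab. Protocol 6.4 allows this only with IDMC recommendation and Sponsor support, and there is no sign that it happened.
- A reader might call the shift table wrong. A shift from baseline to worst grade is naturally read as post-baseline, and the mock-ups in SAP Appendix II are not visible. The wording is ambiguous, not shown to be in error.

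Finally, the worst-grade table openly states that it includes pre-treatment values, and adjacent tables give the post-baseline view. That lowers the weight of the laboratory point. It does not make that table usable as a summary of on-treatment toxicity.

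**Conclusion.** The contradiction is real and visible in the current text. Its consequence depends on which section sites followed, and the documents do not say.

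- Under 7.5.2/7.5.3, new non-serious AEs and unrelated SAEs are lost for up to 70 of the 100 post-treatment days. All-cause TEAE and serious TEAE counts are biased downwards, and newly recorded late serious TEAEs are all related. This would reach the phase 1 primary endpoint.
- Under 8.3.1, in its natural reading, the visible gap is the 2 patients on EO2401 monotherapy. It leaves the phase 1 combination endpoint untouched and affects only the side-by-side display in the randomised extension. It assumes that no redacted qualifier changes the window for that arm.

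Related SAEs are recorded under either rule. The number of missed events cannot be determined from the documents. The point should be corrected, with medium confidence in its practical effect. The worst-grade table is a secondary clarification.

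**What to change.** **Protocol.** Reconcile 7.5.2, 7.5.3, 8.3.1 and 8.5.1 so that the AE collection period and the TEAE window agree in every arm. State explicitly how unrelated SAEs are handled. Leave the indefinite reporting of related SAEs unchanged.

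**Data already collected.**
1. At the data review meeting, review AEs with onset on days 31-100 by site, seriousness and relatedness, to see which rule was applied. The planned listings already carry cohort and center (SAP 7.2). The review already planned in SAP 7.11.2 concerns AEs classed as not treatment-emergent. If the redacted day count is 100, it would not address this period.
2. Add a TEAE/SAE summary limited to 30 days after the last dose, the window collected in all arms, as a descriptive display. SAP 4.3 plans no direct statistical comparison of the groups.
3. Beside it, show the 100-day summary for nivolumab-treated patients, interpreted in the light of step 1.

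**SAP 7.11.3.** Restrict the worst-CTCAE-grade table to values after the first dose. State that the worst grade in the shift table is post-baseline.

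**Cost.** One extra table, one review of existing listings, a date filter, and wording changes that may need an amendment with ethics approval (Protocol 10.9). Events that were never recorded cannot be recovered, so for past data the gain is a correctly labelled summary rather than a complete one.
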